### 7.10.5 Multiplicity

The analysis of the primary endpoint will be performed using a hierarchical hypothesis test in which an alpha of 5% will be preserved for each test. Testing will be employed in the following order:

- CSGI combined versus Placebo (if statistically significant <0.05, then the next hypothesis test will be conducted)
- CSGI high dose versus Placebo (if statistically significant <0.05, then the next hypothesis test will be conducted)
- CSGI low dose versus Placebo (if statistically significant <0.05, then the next hypothesis test will be conducted)
- CSGI high dose versus CSGI low dose

All secondary endpoints and the supportive analyses will be considered as descriptive evidence of efficacy and will be analyzed without any procedures to account for multiple comparisons.

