The primary analysis for the study is the comparison of the change from baseline of plasma epinephrine concentration during induced hypoglycemia with PG <50 mg/dL between CSGI and placebo, and to evaluate if there is a difference between CSGI high dose and low dose versus placebo after 4 weeks of blinded treatment.

The analysis of the primary endpoint will be performed using a two-group t-test for each hypothesis test in the hierarchy, while preserving alpha at 0.05. CSGI (high and low dose combined) will first be tested against placebo, and if the difference is statistically significant  $<0.05$ , CSGI high dose versus placebo will be tested. If statistically significant  $<0.5$ , then CSGI low dose versus placebo will be tested, and if statistically significant, CSGI high dose versus CSGI low dose will be tested.

Analyses of the secondary endpoints including CGM and hormone variables will be conducted with descriptive and inferential statistics. Responses to the Gold scale and hypoglycemia symptom questionnaire will be analyzed using Chi-square tests. The mean endpoints (3-6) from week 4 through the end of study will be presented graphically to assess the time course.

Adverse events, laboratory safety variables (Screening to Day 28), physical examination, vital signs, ECG (Screening to Day 28), and local tolerability data will be reviewed and summarized on an ongoing basis during the study to evaluate the safety of subjects. Safety data will be presented in tabular and/or graphical format and summarized descriptively, where appropriate.

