### **6.1.2.3. Glucagon Infusion Rate Selection**

A previous study (Edelman, ADA annual scientific sessions, 2006) evaluating continuous glucagon administration for the prevention of hypoglycemia tested doses at 2, 4 and 8 ng/(kg\*min) and found apparently no effect at 2 ng/(kg\*min), weak indications of effect at 4 ng/(kg\*min) and, given a modest sample size, reasonably clear effect at 8 ng/(kg\*min) with some but limited room for further effect.

These findings would suggest doses in the vicinity of 4 and 16 ng/(kg\*min) corresponding to 19.2 and 76.8 µg/hr for an 80-kg person would be well chosen in this proof-of-concept study. As further development would most likely lead to a device with a fixed infusion rate, the glucagon doses chosen for the study are 20 and 80 µg/hr, or given the formulation concentration of 5 mg/ml, infusion rates of 4 and 16 µl/hr. For the pump setting that measures in insulin U100 units that corresponds to 0.4 and 1.6 U/hr.

This highest dose to be tested in the study will allow a greater than 10x safety margin based on findings from a 28-day toxicology study in rats conducted with Xeris glucagon (see current Investigator's Brochure).

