### **5 SAMPLE SIZE**

The primary hypothesis is to evaluate change from Induction 1 (baseline visit) to Induction 2 (visit 7, Week 4) in plasma epinephrine concentration after 30 minutes of induced hypoglycemia with plasma glucose  $< 50$  mg/dL between treatment groups. Sample size is based on a closed hierarchical hypothesis test. Using this method, an alpha of 5% will be preserved for each hypothesis test where the next ordered test will only be conducted if statistical significance is achieved for that hypothesis.

Final calculations are based on 80% power and an alpha of 5%, to demonstrate a plasma epinephrine increase compared to placebo of 1.5 nmol/l given a SD of 1.34 nmol/l at an induced PG of 50 mg/dl. Sixteen subjects per treatment group (CSGI high dose, CSGI low dose, and placebo) are required based on the minimum sample size estimate for a comparison.

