### **6 RANDOMIZATION**

The randomization scheme is 1:1:1 for high dose, low dose and placebo. Each group will have 16 subjects, but the placebo group will be matched to high and low infusion rates (8 in each group). The randomization is stratified by site.

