## 7.10 Efficacy Analyses

### 7.10.1 Primary Endpoint

The primary endpoint is the percent change from Induction 1 (baseline visit) to Induction 2 (visit 7, week 4) in plasma epinephrine concentration after 30 minutes of induced hypoglycemia with PG < 50 mg/dL.

Hypotheses of interest:

$H_0: \mu_x = \mu_y$  vs  $H_1: \mu_x \neq \mu_y$

where the treatment comparison of interest (ranked in order of interest) is as follows:

- CSGI Combined vs placebo
- CSGI High vs placebo

- CSGI Low vs placebo
- CSGI High vs CSGI Low

For details regarding multiplicity please see section [7.10.5](#).

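### After the combined test, the fixed order of the three pairwise tests is valid but not needed for the 5% family-wise bound; dropping it would gain power at no cost to that bound

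*SAP*

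**What the plan says.** SAP 7.10.5 and protocol 11.1.1 set the same sequence for the primary endpoint, each step at 5% and each opened only by significance at the step before: (1) combined CSGI versus placebo, (2) high dose versus placebo, (3) low dose versus placebo, (4) high dose versus low dose. The gate to step 4 reads "CSGI low dose versus Placebo (if statistically significant <0.05, then the next hypothesis test will be conducted". The protocol synopsis has the same order, ending with "if statistically significant, CSGI high dose versus CSGI low dose will be tested".

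SAP 7.10.1 lists the four comparisons under "Hypotheses of interest", says that they are ranked by interest, and states a two-sided alternative. SAP 7.10.2 uses a two-group t-test for each.

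Protocol 6.1.2.3 sets the low rate near 4 ng/(kg*min) and the high rate near 16 ng/(kg*min). It reports that an earlier study of hypoglycemia prevention gave "weak indications of effect at 4" ng/(kg*min).

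**The concern.** Under this order, high versus low can be declared only in a trial where the low dose has also beaten placebo. For a given high-dose effect, the weaker the low dose, the larger the difference between doses and the less often the test of that difference opens. If the low dose equals placebo, step 4 opens in at most 5% of trials, however strong the high dose is. Similarly, a chance miss on high versus placebo closes low versus placebo.

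A fixed order normally accepts such losses in return for family-wise control. The question is whether the order of steps 2 to 4 contributes to that control here. If not, the two-dose trial gives up power on a comparison it lists as a hypothesis and gets nothing for it within the 5% bound.

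**Working it through.** **Inputs.** "plasma epinephrine increase compared to placebo of 1.5 nmol/l given a SD of 1.34 nmol/l", 80% power and 5% alpha (SAP section 5); "The randomization scheme is 1:1:1 for high dose, low dose and placebo" and "Each group will have 16 subjects" (SAP section 6); two-sided tests (SAP 7.10.1); two-group t-tests (SAP 7.10.2). The documents give no separate effect for either dose. Effects other than +1.5 are assumptions, shown over a range.

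**The plan's own figure.** The normal approximation gives n = 2(1.960 + 0.842)² × (1.34/1.5)² ≈ 2 × 7.849 × 0.798 = 12.5, so 13 per arm. The exact two-sided t-test needs 14 per arm (power 81.3%), and 3 × 14 = 42, which is the minimum N in the synopsis. At the 16 per arm randomized, a single comparison has 86.5% power.

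**Error control.** Write H, L and P for the three means. The nulls are C: (H+L)/2 = P; HP: H = P; LP: L = P; HL: H = L. Take them in pairs:
- Any two of HP, LP and HL give H = L = P at once.
- C with HP gives L = P. C with LP gives H = P. C with HL gives H = L = P.

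So any two true nulls mean that all three means are equal, and only two cases remain:
- All means equal. Nothing is rejected unless step 1 is, and step 1 is a 5% test of exactly this state. Family-wise error is at most 5%.
- Means not all equal. At most one null is true, and its own 5% test bounds the error.

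Neither case uses an order among HP, LP and HL. If dropout is unequal, C becomes a weighted mean with positive weights and the argument is unchanged. Every rejection the sequence makes needs step 1 and that pairwise test to be significant, so the unordered rule makes it too.

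**Simulation.** 400,000 trials per setting, 16 per arm, SD 1.34, pooled-variance t-tests, step 1 as 32 versus 16. Effects are in nmol/l relative to placebo.

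| High | Low | Step 1 passes | High vs low declared, ordered | Unordered | Low vs placebo declared, ordered | Unordered |
|---|---|---|---|---|---|---|
| 1.5 | 0 | 35.6% | 1.3% | 30.3% | 2.5% | 2.5% |
| 1.5 | 0.375 | 56.3% | 3.9% | 34.9% | 11.5% | 11.6% |
| 1.5 | 0.75 | 74.8% | 5.5% | 24.7% | 32.4% | 33.4% |
| 1.5 | 1.0 | 84.1% | 4.8% | 14.7% | 50.6% | 53.2% |
| 2.0 | 0.5 | 79.3% | 12.1% | 68.2% | 17.5% | 17.5% |
| 3.0 | 1.5 | 99.9% | 73.4% | 86.5% | 86.5% | 86.5% |
| 1.5 | 1.5 | 94.7% | 2.7% (false) | 4.8% (false) | 77.9% | 85.7% |

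High versus placebo is the same under both rules.

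Family-wise error, ordered / unordered:
- all means equal: 5.0% / 5.0%
- high +1.5, low 0: 2.5% / 2.5%
- both +1.5: 2.7% / 4.8%
- both +3: 5.0% / 5.0%
- high +1, low −1: 2.2% / 2.2%

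Without step 1 the error is 13.0% when all means are equal, so step 1 has to stay. In that same state, the chance of two or more false rejections rises from 2.6% to 4.3% when the order is dropped.

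**The case against.** The strongest reply is that the order is deliberate. SAP 7.10.1 ranks the comparisons by interest with high versus low last, the primary objective is CSGI versus placebo, and no listed objective names a comparison between doses. Putting the lowest-ranked comparison last is what a fixed sequence is for. This stands: the plan is valid and coherent as written. It does not show that the order is needed, since step 1 alone supplies the protection.

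Three further limits stand:
- **Scale.** The gated endpoint in the SAP is percent change, and the documents give no SD for it. The powers above are for absolute change, which SAP section 10 moved to secondary and SAP 7.10.5 leaves without multiplicity adjustment. A descriptive dose comparison on that scale is not gated. The error argument does not depend on scale.
- **Step 1 still binds.** With an inactive low dose, the pooled difference halves to 0.75 and step 1 passes in only 35.6% of trials, which caps what reordering can recover.
- **Attained error.** The 5% maximum does not move, but error below it can rise, as shown.

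A reader might go further and infer that the trial cannot formally conclude that the doses differ. The documents do not support that: with high +3 and low +1.5 the sequence declares it in 73% of trials. Nor do they support taking the low dose as inactive. Protocol 6.1.2.3 reports weak indications for another outcome, not zero effect on epinephrine. A reader might also infer that a weak low dose loses power for low versus placebo through the ordering. It loses essentially nothing; that loss arises when both doses are active.

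**Conclusion.** The point holds as a free improvement. The fixed sequence is not an error, but its order after step 1 is unnecessary for the 5% family-wise bound and costs power. The cost to high versus low is large when the high dose is active and the low dose weak, and smaller when both clearly beat placebo. Low versus placebo gains about 8 percentage points when both doses are at the planned +1.5; as ordered, its 78% is below the 80% design power.

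The error result rests on three arms, step 1 kept as the gate, and each t-test holding its 5% level. Unequal variances can disturb step 1 (11.2% when the placebo SD is doubled and all means are equal), but equally under both rules. The power figures rest on the absolute-scale SD and on assumed dose effects.

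**What to change.** Before the treatment-group unblinding for the Day 27 analysis (SAP section 8), keep step 1 in SAP 7.10.5 and replace steps 2 to 4 with: *If step 1 is significant, high vs placebo, low vs placebo and high vs low are each tested at two-sided 5% with no further ordering.* A sentence may be added that with three arms this closed procedure holds the family-wise error at 5%.

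Align SAP 7.10.1 and list the change in SAP section 10. Either align protocol 11.1.1 and the synopsis, or rely on the precedence that protocol section 11 and SAP section 2 give the SAP. If the synopsis is edited, also reconcile its threshold for the high-dose step, printed as 0.5 against 0.05 in protocol 11.1.1 and SAP 7.10.5.

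The cost is wording, plus IRB review under protocol 16.1 if the protocol itself is amended. No patients or data are added, and no test loses power. The price is a higher attained error within the 5% bound.

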### 7.11 Safety Analyses

The safety analyses will be presented by the treatment received for the Safety Analysis Population.

#### 7.11.1 Adverse Events

A treatment emergent adverse event (TEAE) is defined as:

- Any AE that has an onset on or after the first dose of study drug or
- Any pre-existing AE that has worsened in severity on or after the first dose of study drug.

A treatment-related AE is defined as an AE as being related to the study drug if response to “Is there a reasonable possibility that the drug caused the event?” is Yes. If an AE has missing relationship it is assumed to be related to the study drug for analysis purposes.

Maximum severity will be assumed for an AE with missing severity.

The following tables will be presented for AEs:

- Overall incidence and the number of AEs, SAEs, TEAEs leading to withdrawal.
- TEAE by system organ class and preferred term, incidence and number of events
- Treatment-related TEAE by system organ class and preferred term, incidence and number of events
- Serious TEAE by system organ class and preferred term, incidence and number of events
- TEAE by system organ class, preferred term and maximum severity, incidence
- Treatment related TEAE by system organ class, preferred term and maximum severity, incidence
- TEAEs leading to early withdrawal by system organ class and preferred term, incidence
- Listing of Serious TEAEs (presented in the Table section of the appendices)
- Listing of Deaths (presented in the Table section of the appendices)

All AEs will be listed.

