**Study Schematic**

After a run-in on CGM, subjects will have key hormones of their hypoglycemia counter regulatory response quantified using a stepwise hypoglycemia induction. They will then receive investigational product for 4 weeks before discontinuation and reassessment of the same hypoglycemia counter regulatory response.

Treatment stops at 4 weeks, but subjects will continue blinded for 6 additional months to investigate duration of response with assessments at 3 and 6 months.

Study location:	Approximately 6-8 clinical research centers in the United States.
Study duration:	The estimated duration of study participation for individual subjects is approximately 7.5 months. The estimated duration of the entire study is 1 year from first patient in to last patient out.
Sample size:	
The primary hypothesis is to evaluate change from baseline to 4 weeks of plasma epinephrine concentration after 30 minutes of induced hypoglycemia with plasma glucose <50mg/dL between treatment groups. Sample size is based on a hierarchical hypothesis test in which the comparison of treatment groups will be implemented in the following order:
 
 
CSGI (combined groups -high and low dose) versus placebo
 
CSGI high dose versus placebo
 
CSGI low dose versus placebo
 
CSGI high dose versus CSGI low dose
 

	Using this method, an alpha of 5% will be preserved for each hypothesis test where the next ordered test will only be conducted if statistical significance is achieved for that hypothesis. Final calculations are based on 80% power and an alpha of 5%, to demonstrate a plasma epinephrine increase compared to placebo of 1.5 nmol/l given and SD of 1.34 nmol/l at an induced PG of 50 mg/dl. Sixteen subjects per group (CSGI high dose, CSGI low dose, and placebo) are required based on the minimum sample size estimate for a comparison against placebo (N=42). To account for attrition, a total of 48 subjects will be randomized for the study.
Subjects:	Male or female type 1 diabetes mellitus patients with recurrent severe hypoglycemic episodes indicative of hypoglycemia associated autonomic failure (HAAF) ages 21-64 years, inclusive.

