#### **6.4. Clinical Experience with Glucagon**

Glucagon has a long history of medical use in the US, and is currently marketed by Eli Lilly & Co. as Glucagon (Glucagon Injection [rDNA origin]), and Novo Nordisk as GlucaGen® HypoKit®, both RLDs for treatment of severe hypoglycemia. Glucagon has a rapid onset of action and an extremely short half-life, and its safety, efficacy and clinical pharmacology have been well established [[FDA CDER #2](#)]. The Agency first approved glucagon for use in humans in 1960.

[figure not shown]
Since 2013 when the first IND for Xeris formulation went into effect, multiple clinical studies have been successfully completed including two studies utilizing the Omnipod for delivery. Details are provided in Xeris' current Investigator's Brochure.

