### **10.5. Definition of an Adverse Event**

An AE is any untoward medical occurrence in a clinical investigation subject administered a pharmaceutical product and which is not necessarily required to have a causal relationship with this treatment. An AE can therefore be any unfavorable and unintended sign, symptom, or disease temporally associated with the use of a medicinal product, whether or not considered related to the medicinal product. Examples of AEs include:

- Abnormal test findings.
- Clinically significant symptoms and signs.
- Changes in physical examination findings which are untoward and deemed clinically significant by the investigator.
- Allergy/hypersensitivity.

The criteria for determining whether an abnormal objective test finding may be reported as an AE are as follows:

- Test result is associated with accompanying symptoms,
- Test result requires additional diagnostic testing or medical/surgical intervention,
- Test result leads to a change in study dosing or discontinuation from the study, significant additional concomitant drug treatment or other treatment.

- Test result is considered to be an AE by the investigator or Sponsor.

Repeat of a test based on an abnormal result in the absence of the above conditions does not constitute an AE. Any abnormal test result determined to be an error does not require reporting as an AE.

A treatment-emergent AE (TEAE) is an AE that either commenced following initiation of study treatment or was present prior to study treatment but increased in frequency or severity following initiation of study treatment.

Standard medical terminology should be used in describing AEs. Informal descriptions should be avoided.

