## **10.7. Reporting Period**

For all AEs, the reporting period to Xeris Pharmaceuticals begins from the subject providing informed consent, through the last subject Visit. All adverse events will be followed until resolution or the subject is medically stable.

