## **11.3. Safety Analysis**

All safety analyses will be performed using the safety analysis population.

The following variables will be compared between the treatments for safety purposes:

- Adverse events and serious adverse events (Screening to Final Visit)
- Laboratory safety variables (Screening to Final Visit)
- Physical examination (Screening to Final Visit)
- Vital signs (Screening to Final Visit)
- Body weight (Screening to Final Visit)
- ECG (Screening to Final Visit)
- Local tolerability, including:
  - Subjective injection site discomfort as reported by subjects using a 100-mm VAS and ordinal pain scales ([Appendix 3](#)).
  - Erythema and or edema formation at site of injection assessed using the Draize scale ([Appendix 4](#)).

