## 12 LIST OF TABLES, FIGURES AND LISTINGS

The following table includes details of the tables, figures and listings (TFLs) for the study. Those marked with an asterisk (\*) are planned for the primary endpoint analysis and presentation of the accompanying safety analysis for that time period (See Section 8).

Table Number	Table Title	Shell Number (if repeat)
14.1.1.1*	Summary of Subject Disposition - All Subjects	
14.1.1.2*	Summary of Analysis Populations - All Randomized Subjects	
14.1.2*	Summary of Protocol Deviations - Intent-to-Treat Population	
14.1.3.1*	Summary of Demographic and Baseline Characteristics - Safety Population	
14.1.3.2*	Summary of Demographic and Baseline Characteristics - Intent-to-Treat Population	14.1.3.1
14.1.3.3*	Summary of Demographic and Baseline Characteristics - Per Protocol Population	14.1.3.1
14.1.4*	Summary of Medical History - Intent-to-Treat Population	
14.2.1.1*	Percent change from Induction 1 (Baseline visit) to Induction 2 (Visit 7, Week 4) in Plasma Epinephrine Concentration During Induced Hypoglycemia with PG <50 mg/dl Intent-to-Treat Population	
14.2.1.2*	Percent change from Induction 1 (Baseline visit) to Induction 2 (Visit 7, Week 4) in Plasma Epinephrine Concentration During Induced Hypoglycemia with PG <50 mg/dl Per Protocol Population	14.2.1.1
14.2.1.3*	Percent change from Induction 1 (Baseline visit) to Induction 2 (Visit 7, Week 4) in Plasma Epinephrine Concentration During Induced Hypoglycemia with PG <50 mg/dl, Sensitivity analysis 1* Per Protocol Population	14.2.1.1
14.2.1.4*	Percent change from Induction 1 (Baseline visit) to Induction 2 (Visit 7, Week 4) in Plasma Epinephrine Concentration During Induced Hypoglycemia with PG <50 mg/dl, Sensitivity analysis 2* Per Protocol Population	14.2.1.1
14.2.1.5*	Percent change from Induction 1 (Baseline visit) to Induction 2 (Visit 7, Week 4) in Plasma Epinephrine Concentration During Induced Hypoglycemia with PG <50 mg/dl, Sensitivity analysis 3* Per Protocol Population	14.2.1.1
14.2.2.1.1*	Absolute change from Induction 1 (Baseline visit) to Induction 2 (Visit 7, Week 4) in Plasma Epinephrine Concentration During Induced Hypoglycemia with PG <50 mg/dl Intent-to-Treat Population	14.2.1.1

Table Number	Table Title	Shell Number (if repeat)

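### The TEAE window has no end date, so the final by-arm TEAE tables pool 4 weeks on drug with 22 to 26 drug-free weeks and dilute an on-drug contrast

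*SAP*

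**What the plan says.** SAP 7.11.1 has two limbs. The first is "Any AE that has an onset on or after the first dose of study drug". The second, for conditions already there before dosing, is "Any pre-existing AE that has worsened in severity on or after the first dose of study drug". Neither has an upper limit. Protocol 10.5 is equally open: a TEAE "is an AE that either commenced following initiation of study treatment", or one that got worse after that point.

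Collection is long. Under Protocol 10.7 the AE reporting period "begins from the subject providing informed consent, through the last subject Visit", and Protocol 11.3 compares AEs between treatments from screening to the final visit. The design is short treatment with long follow-up: "Treatment stops at 4 weeks, but subjects will continue blinded for 6 additional months" (Protocol, Study Schematic).

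The AE tables in SAP 7.11.1 and SAP 12 are split by system organ class, preferred term, severity, causality and seriousness. None is split by period, and no exposure-adjusted rate is planned. The one pointer to a time limit is in SAP 12, where starred outputs are planned for the primary endpoint analysis and "presentation of the accompanying safety analysis for that time period". The starred AE tables are 14.3.1.1 (overview), 14.3.1.2 (TEAE by SOC and preferred term), 14.3.1.4 (serious TEAE), 14.3.1.9 (TEAE by relationship) and 14.3.2.2 (SAEs).

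**The concern.** A TEAE table by arm is read as the comparison of what happened under drug and under placebo. Here most of the time behind the final tables is after drug has stopped. Background events then accumulate in all arms for about half a year, and the proportion of subjects with at least one event approaches its ceiling everywhere.

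The follow-up also generates events of its own. Visits 9 and 11 repeat the induced hypoglycemia procedure, with lines in both arms, months after the last dose. AEs from those procedures count as treatment-emergent. So does hypoglycemia that meets the SAE criteria, which Protocol 10.6 keeps reportable.

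At stake is the between-arm safety reading of a 48-subject trial that has no data and safety monitoring board (SAP 9).

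**Working it through.** **Inputs from the documents.** Treatment lasts 4 weeks. Follow-up runs to 26 weeks after completing treatment (Protocol 7.1). Protocol 9.5 instead times visits from randomization, which puts Visit 11 (Week 26) 22 weeks after treatment. Participation is about 7.5 months and the whole study 1 year (Synopsis). Allocation is 16:16:16, so combined CSGI against placebo is 32 against 16 (SAP 6). The AE section gives no figure to reproduce.

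**Which follow-up length fits the stated participation time?** With 25 days of screening, 4 weeks and 26 weeks: (25 + 28 + 182)/30.44 = 7.7 months. With Week 26 counted from randomization: (25 + 182)/30.44 = 6.8 months. The stated 7.5 is closer to the first. Both are carried below.

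**Drug-free share of post-dose time.** 26/30 = 87%, or 22/26 = 85%.

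**Dilution of an event rate ratio.** With on-drug ratio r, and a ratio of 1 after stopping, the pooled ratio is (4r + 26)/30 or (4r + 22)/26. It does not depend on the background rate.

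- r = 2: 34/30 = 1.13, or 30/26 = 1.15.
- r = 3: 38/30 = 1.27, or 34/26 = 1.31.

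**Dilution of incidence.** This needs a background rate, which the documents do not give. Assume a constant rate b per 28 days, doubled on drug. Incidence is 1 − exp(−expected events). Expected events over 4 + 26 weeks (7.5 periods of 28 days) are 7.5b on placebo and 8.5b on CSGI. Over 4 + 22 weeks (6.5 periods) they are 6.5b and 7.5b.

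| b | 4 weeks on drug | 4 + 26 weeks | 4 + 22 weeks |
|---|---|---|---|
| 0.1 | 9.5% v 18.1% | 52.8% v 57.3% | 47.8% v 52.8% |
| 0.2 | 18.1% v 33.0% | 77.7% v 81.7% | 72.7% v 77.7% |
| 0.3 | 25.9% v 45.1% | 89.5% v 92.2% | 85.8% v 89.5% |

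The pooled difference equals the 4-week difference times exp(−6.5b) for 26 drug-free weeks. At b = 0.2 that is 14.8 × 0.273 = 4.0 points. If the rate is tripled on drug at b = 0.2, 18.1% v 45.1% (27.0 points) becomes 77.7% v 85.0% (7.4 points).

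**Rare preferred term.** Assume a background of 0.01 per 28 days and an on-drug rate of 0.30. On treatment: 1.0% v 25.9%, a difference of 24.9 points. Over 30 weeks: 1 − exp(−0.075) = 7.2% v 1 − exp(−0.365) = 30.6%, a difference of 23.4 points. The absolute signal barely moves.

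**Event counts.** At b = 0.2 with a doubling, events per subject are 0.2 v 0.4 over 4 weeks and 1.5 v 1.7 over 30 weeks. The excess is 0.2 in both. Under a Poisson assumption with 32 v 16 subjects, its standard error is √(0.4/32 + 0.2/16) = 0.16 on treatment and √(1.7/32 + 1.5/16) = 0.38 over 30 weeks. The excess is kept, but the noise more than doubles.

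**The Week 4 cut.** The primary analysis runs when the last subject's data for that visit are complete. A 1-year study with 7.5 months per subject implies about 4.5 months of enrolment, or 4.5 × 52/12 ≈ 19 to 20 weeks. The earliest subjects could have that much drug-free time by then. SAP 8 and SAP 12 do not say whether it is included.

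**The case against.** The open window is the same in both documents and may be a deliberate, inclusive choice. All AEs are listed, so nothing is lost. The starred outputs can naturally be read as limited to the treatment period, in which case much of the on-treatment picture is already planned. SAP 7.11.1 also asks for numbers of events in the TEAE, treatment-related and serious tables, and counts do not saturate. Local tolerability is assessed separately at treatment-period visits. Non-serious hypoglycemia, and injection-site reactions that need no intervention, are not AEs at all (Protocol 10.6), which lowers the background.

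Most of this stands, and it limits the point. It does not remove it. The treatment-related table (14.3.1.3), the severity tables (14.3.1.8.1 and 14.3.1.8.2) and the discontinuation tables (14.3.1.5 and 14.3.2.3) are not starred, so they exist only in pooled form. The severity and withdrawal tables are specified as incidence only, without counts. Causality tables separate the periods only through investigator judgement, and missing causality is counted as related. The starred tables still lack a per-subject rule, so two programmers could produce different results from the same text.

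A reader might infer that the post-treatment weeks can be set aside because "Glucagon has a rapid onset of action and an extremely short half-life" (Protocol 6.4). That sentence describes glucagon as marketed for severe hypoglycemia, not 28 days of continuous infusion. The trial itself looks for lasting effects at 3 and 6 months and samples anti-glucagon antibody at Visits 9 and 11. Post-treatment events should stay in view.

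**Conclusion.** The gap is real and worth closing, at the level of a recommended change. Both documents leave the TEAE window open. The final by-arm TEAE tables then rest on 85% to 87% drug-free time. A doubling of the event rate on drug appears as a ratio of 1.13 to 1.15, whatever the background rate. Differences in overall or common-event incidence can be largely masked. The size of that masking rests on assumed rates (0.1 to 0.3 background events per 28 days, constant hazard, no excess after stopping).

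Three stronger readings are tempting, and the documents do not support them.

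- That a true on-drug excess disappears. For rare preferred terms the absolute difference is almost unchanged, and event counts keep the excess.
- That every AE table uses the open TEAE definition. The overview also counts AEs and SAEs, and 14.3.1.6, 14.3.1.7 and 14.3.2.2 are SAE tables not labelled treatment-emergent.
- That the Week 4 tables will contain off-drug events. The SAP is silent, so this is an ambiguity, not a stated rule.

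**What to change.** In SAP 7.11.1, add an on-treatment flag: onset or worsening from first dose to last dose plus a short window, prespecified and justified. State how events during the Visit 7 induction, which follows pod removal, are assigned. The documents give no AE window to borrow. The only post-dose interval they state is 30 days, for death reporting (Protocol 10.13). For illustration, a true ratio of 2 would show as (8 + 1)/5 = 1.80 with a 7-day window and (8 + 4.29)/8.29 = 1.48 with a 30-day window.

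Use the flag as the per-subject cut-off for the starred Week 4 safety tables, which gives the time period in SAP 12 a meaning. In the final report, present the overall, SOC and preferred term, treatment-related, severity and serious TEAE tables by arm for the on-treatment and post-treatment periods separately. Keep the existing whole-study tables beside them, so that early post-stop and late events, including any immune ones, are not displaced. Reconcile Protocol 7.1 with 9.5 on whether Week 26 runs from the end of treatment or from randomization.

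The cost is one derived variable, repeat table shells and smaller counts per period. No new data are needed.
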